3.9.3.4 Withdrawal of Consent

All subjects (and subjects' legal representatives if subjects are minors or are hospitalized for reasons of medical protection) have the right to withdraw their consent from further participation in the trial at any time without prejudice. Subjects (and subjects' legal representatives if subjects are minors or are hospitalized for reasons of medical protection) cannot withdraw consent for use of data already collected as part of the trial, but only for future participation. The investigator or subinvestigator can also discontinue a subject's participation in the trial at any time if medically necessary. Unless the subject (and the subject's legal representative if the subject is a minor or is hospitalized for reasons of medical protection) provides their written withdrawal of consent or there is other written documentation by the investigator or subinvestigator confirming the verbal intent of the subject (and the subject's legal representative if the subject is a minor or is hospitalized for reasons of medical protection) to completely withdraw from the trial, subjects should be followed for all protocol-specified evaluations and assessments, if possible.

Complete withdrawal of consent requires refusal by a subject (and the subject's legal representative if the subject is a minor or is hospitalized for reasons of medical protection) of ALL of the following methods of follow-up (these methods of follow-up will also be noted in the trial ICF):

- Participation in all follow-up procedures specified in the protocol (whether in-clinic, by telephone, or by an in-home visit).
- Participation in a subset of protocol specified follow-up procedures (by a frequency schedule and method, as agreed by subject and staff).
- Contact of the subject by trial personnel, even if only by telephone, to assess current medical condition, and obtain necessary medical or laboratory reports relevant to the trial's objectives.
- Contact of alternative person(s) who have been designated in source records as being available to discuss the subject's medical condition, even if only by telephone, mail, or e-mail (eg, family, spouse, partner, legal representative, friend, neighbor, or physician).
- Access to medical information from alternative sources (eg, hospital/clinic medical records, referring doctor's notes, public records, dialysis, transplantation or vital registries, social media sources).

Withdrawal of consent is a critical trial event and therefore should be approached with the same degree of importance and care as is used in initially obtaining informed consent. The reasons of a subject (and the subject's legal representative if the subject is a minor or is hospitalized for reasons of medical protection) for an intended withdrawal need to be completely understood, documented, and managed to protect the rights of the subject and the integrity of the trial. A subject (and the subject's legal representative if the subject is a minor or is hospitalized for reasons of medical protection) may initially express their desire to discontinue IMP administration, which is not equivalent to a complete withdrawal of consent for further participation (see Section 3.9.3.1 Treatment Discontinuation). A subject (and the subject's legal representative if the subject is a minor or is hospitalized for reasons of medical protection) may, however, indicate that further trial participation is creating a burden on their work or social schedule. Therefore, the investigator or subinvestigator should follow the procedures outlined in Section 3.9.3.3 Documenting Reasons for Discontinuation to determine if the subject can continue participation in the trial if modifications to his/her treatment and/or schedule of assessments can be accommodated. Only subjects (and subjects' legal representatives if subjects are minors or are hospitalized for reasons of medical protection) who withdraw their permission for all of the above degrees of follow-up are considered to have completely withdrawn their consent to participate in the trial.

3.9.3.5 Procedures to Encourage Continued Trial Participation

In all cases of impending IMP discontinuation or consent withdrawal, investigators or subinvestigators will be given instructions to meet and discuss with the subject (and the subject's legal representative if the subject is a minor or is hospitalized for reasons of medical protection) their options of continuing in the trial, preferably on therapy. The

investigator or subinvestigator should ensure understanding and documentation of the reasons why the subject (and the subject's legal representative if the subject is a minor or is hospitalized for reasons of medical protection) wishes to withdraw consent.

3.10 Screen Failures

A screen failure subject is one from whom informed consent is obtained and is documented (ie, subject signs an ICF), but who is not enrolled in the trial prior to IMP administration on Day 1 of Period 1 in each cohort.

It is permissible for subjects who sign an ICF but who are not enrolled in the trial prior to IMP administration on Day 1 of Period 1 to be rescreened. In the event that rescreening is not completed within the original screening period, consent must be newly obtained and a new subject identifier must be assigned. However, for those subjects who were withdrawn from the trial at the discretion of the sponsor and who agree to take part in the trial again and sign the ICF again, but who are not enrolled in the trial prior to IMP administration on Day 1 of their scheduled treatment period (Period 2 or 3), the same subject identifier as the original will also be used for the repeated rescreening.

For screen failures, the following information will be recorded on the source documents and screen failure-specific eCRF:

Subject identifier, date of visit, date of obtaining informed consent, date of birth, sex, date of screen failure determination, reason for screen failure, country (Japan), race, and ethnicity.

3.11 Definition of Completed Subjects

The trial period is defined as the time period during which subjects are evaluated in regard to the primary objectives of the trial irrespective of whether the subject actually receives all doses of the IMP. Subjects who complete the last scheduled sampling for PK assessments for the PK trial will be defined as trial completers. For the purposes of this trial, subjects who complete assessment on Day 14 of Period 3 in Cohort 1 or Cohort 1' (as necessary) (single administration period) or on Day 42 of Period 2 in Cohort 2 (repeated administration period) will be defined as trial completers.

3.12 Definition of Subjects Lost to Follow-up

Subjects who cannot be contacted during or before the treatment period and those who do not have a known reason for discontinuation (eg, withdrawal of consent or AE, etc.) will be defined as subjects lost to follow-up.

The investigator, subinvestigator, or designee will make 3 documented attempts to contact the subject by telephone and in the event the site is unable to reach the subject by telephone, the site will attempt to contact the subject via certified mail or an alternative similar method where appropriate, before assigning a "lost to follow-up" status. If a subject becomes lost to follow-up, the results of the investigation (whether or not the subject was contacted, occurrence or non-occurrence of AEs, date of contact, method of contact) will be recorded in the source data and the eCRF.

3.13 Subject Compliance

The time of administration and the dose of each IMP will be recorded on the source documents and eCRF. Information on missed doses and whether the IMP was taken in an inappropriate manner will also be recorded on the source documents and eCRF. An oral check will be performed immediately after IMP administration to ensure that the subject has swallowed the IMP.

3.14 Protocol Deviations

In the event of a significant deviation from the protocol due to an emergency, accident, or mistake (eg, violation of informed consent process, IMP dispensing or subject dosing error, treatment assignment error, subject enrolled in violation of eligibility criteria or concomitant therapy criteria), the investigator, subinvestigator, or designee will contact the sponsor at the earliest possible time by telephone. The investigator or subinvestigator and sponsor will come as quickly as possible to a joint decision regarding the subject's continuation in the trial. This decision will be documented by the investigator or subinvestigator and the sponsor, and reviewed by the site monitor.

4 Restrictions

4.1 Prohibited Medications

The use of the following drugs between each specified date and the completion of assessment on Day 14 of Period 3 in Cohort 1 or Cohort 1' (as necessary) (single administration period) or on Day 42 of Period 2 in Cohort 2 (repeated administration period) or the completion of ET assessment is prohibited:

- CYP2D6 inhibitors and CYP3A4 inhibitors and inducers listed in Appendix 3 (from 14 days prior to IMP administration in Period 1^{*}), excluding the topical agents listed in Appendix 4 for which concomitant use with the IMP is permitted.
- Rexulti tablets (from 21 days prior to IMP administration in Period 1^{*})
- Clozapine (from informed consent)
- Adrenaline (from 28 days prior to IMP administration in Period 1^{*})

- Other investigational medicinal products under development (unapproved drugs) (from 60 days prior to IMP administration in Period 1^{*})
- * For subjects who were withdrawn from the trial at the discretion of the sponsor and resume participation in the trial from Period 2 or 3, the use of the drugs is prohibited from 14, 21, 28, and 60 days, respectively, before IMP administration in the treatment period (Period 2 or 3) in which they are to resume participation in the trial.

4.2 **Prohibited Therapies**

The use of the following therapy between 60 days prior to IMP administration in Period 1^* of each cohort and the completion of assessment on Day 14 of Period 3 in Cohort 1 or, Cohort 1' (as necessary) (single administration period) or on Day 42 of Period 2 in Cohort 2 (repeated administration period) or the completion of ET assessment is prohibited:

- Electroconvulsive therapy
- * For subjects who were withdrawn from the trial at the discretion of the sponsor and resume participation in the trial from Period 2 or 3, the use of the therapy is prohibited from 60 days before IMP administration in the treatment period (Period 2 or 3) in which they are to resume participation in the trial.

4.3 Restricted Medications

The use of the following drugs between Day 1 of Period 1^{*} of each cohort and the completion of assessment on Day 14 of Period 3 in Cohort 1 or Cohort 1' (as necessary) (single administration period) or on Day 42 of Period 2 in Cohort 2 (repeated administration period) or the completion of ET assessment is restricted:

* For subjects who were withdrawn from the trial at the discretion of the sponsor and resume participation in the trial from Period 2 or 3, the use of the drugs is restricted from Day 1 of IMP administration in the treatment period (Period 2 or 3) in which they are to resume participation in the trial.

• Other antipsychotic drugs

The use of other antipsychotic drugs at a steady dose and regimen will be permitted within the dosing range indicated below. The dose or frequency may be reduced at the discretion of the investigator or subinvestigator in response to symptom improvement or maintenance or from a safety perspective. Upper limit of dose and regimen

- Antipsychotic medication comprising no more than two active components
- A daily dose equivalent to no more than 600 mg/day of chlorpromazine
 - If multiple antipsychotics are taken in the same day, this is to be the combined equivalent dose.

• Chlorpromazine equivalent doses are based on the conversion values listed in Appendix 5.

However, this does not include administration of antipsychotic medication at doses equivalent to less than 100 mg/day of chlorpromazine, which are not expected to have any antipsychotic effect.

• Antiparkinsonian drugs

The use of antiparkinsonian drugs will be permitted only when the subject has extrapyramidal symptoms and the investigator or subinvestigator concludes that these drugs should be used. In that case, the dose and regimen should comply with the package insert. However, preventive use will be prohibited. Therefore, subjects who have no extrapyramidal symptoms but are taking antiparkinsonian drugs at the time of informed consent must temporarily discontinue the medication. Extrapyramidal symptoms should be assessed using DIEPSS prior to new use or dose increase of an antiparkinsonian drug. It is not permitted for any antiparkinsonian drug to be administered within 12 hours prior to DIEPSS assessment.

• β-Blockers

The use of β -blockers will be permitted only for the treatment of nonpsychiatric complications (eg, cardiovascular disorders) and only if the dose and regimen remain unchanged from before participation in the trial.

4.4 Other Restrictions

- The consumption of foods and beverages containing grapefruit, Seville orange, or star fruit between 7 days prior to IMP administration in Period 1* of each cohort and the completion of assessment on Day 14 of Period 3 in Cohort 1 or Cohort 1' (as necessary) (single administration period) or on Day 42 of Period 2 in Cohort 2 (repeated administration period) or the completion of ET assessment is prohibited.
- The consumption of foods and beverages containing St. John's Wort, Ginkgo biloba, goldenseal, or echinacea (Echinacea purpurea) between 14 days prior to IMP administration in Period 1* of each cohort and the completion of assessment on Day 14 of Period 3 in Cohort 1 or Cohort 1' (as necessary) (single administration period) or on Day 42 of Period 2 in Cohort 2 (repeated administration period) or the completion of ET assessment is prohibited.
- * For subjects who were withdrawn from the trial at the discretion of the sponsor and resume participation in the trial from Period 2 or 3, the consumption of these foods and beverages is prohibited from 7 and 14 days, respectively, before IMP administration in the treatment period (Period 2 or 3) in which they are to resume participation in the trial.

5 Reporting of Adverse Events

5.1 Definitions

An AE is defined as any untoward medical occurrence in a patient or clinical trial subject administered a medicinal product and which does not necessarily have a causal relationship with this treatment. Adverse events would not include information recorded as complications at screening for preplanned procedures for which the underlying condition was known and no worsening occurred. An adverse drug reaction is any untoward and unintended response to an IMP related to any dose administered.

A suspected adverse reaction is any AE for which there is a reasonable possibility that the IMP caused the AE.

An SAE includes any event that results in any of the following outcomes:

- Death
- Life-threatening; ie, the subject was, in the opinion of the investigator or subinvestigator, at immediate risk of death from the event as it occurred. It does not include an event that, had it occurred in a more severe form, might have caused death.
- Persistent or significant incapacity/disability or substantial disruption of the ability to conduct normal life functions.
- Requires inpatient hospitalization or prolongs hospitalization
 - Hospitalization itself should not be reported as an SAE; whenever possible the reason for the hospitalization should be reported.
 - Hospitalizations or prolonged hospitalizations for social admissions (ie, those required for reasons of convenience or other nonmedical need) are not considered SAEs.
- Congenital anomaly/birth defect.
- Other medically significant events that, based upon appropriate medical judgment, may jeopardize the subject and may require medical or surgical intervention to prevent one of the outcomes listed above, eg, allergic bronchospasm requiring intensive treatment in an emergency room or home, blood dyscrasias or convulsions that do not result in hospitalization, or the development of drug dependency or drug abuse.

Nonserious AEs are all AEs that do not meet the criteria for a "serious" AE.

Immediately Reportable Event (IRE):

- Any SAE
- Any AE related to occupational exposure.

Confidential - Proprietary Information

- Potential serious hepatotoxicity (see Section 5.4 Potential Serious Hepatotoxicity)
- Pregnancies are also defined as IREs. Although normal pregnancy is not an AE, it will mandate IMP discontinuation and must be reported on an IRE form to the sponsor. Pregnancy will only be recorded on the AE eCRF if there is a complication or abnormality in the newborn.

Clinical Laboratory Assessment Value Changes: It is the investigator's or subinvestigator's responsibility to review the results of all laboratory tests as they become available. This review will be documented by the investigator's or subinvestigator's dated signature on the laboratory report. For each abnormal laboratory test result, the investigator or subinvestigator needs to verify whether this is an abnormal (ie, clinically relevant) change from baseline for that individual subject. This determination, however, does not necessarily need to be made the first time an abnormal value is observed. The investigator or subinvestigator may repeat the laboratory test or request additional tests to verify the results of the original laboratory tests. If this laboratory value is considered clinically relevant by the investigator or subinvestigator (eg, subject is symptomatic, requiring corrective treatment or further evaluation), or if the laboratory value leads to discontinuation or meets the criteria for an SAE, this is considered an AE.

Severity: Adverse events will be graded on a 3-point scale and reported as indicated on the eCRF. The intensity of an AE is defined as follows:

- 1 = Mild: Discomfort noticed, but no disruption to daily activity.
- 2 = Moderate: Discomfort sufficient to reduce or affect normal daily activity.
- 3 = Severe: Inability to work or perform normal daily activity.

IMP Causality: Assessment of causal relationship of an AE to the use of IMP is defined as follows:

Related: There is a reasonable possibility of a temporal and causal relationship between the IMP and the AE.

Not related: There is no temporal or causal relationship between the IMP and the AE.

Date of Onset and Recovery (for diarrhea and vomiting, date and time of onset and date and time of recovery):

Date of onset: The date of onset of an AE or date of confirmation of an AE. If the severity or seriousness of the reported event changes, the date of exacerbation will be taken as the "date of onset of AE."

Date of recovery: The date of recovery of an AE or date of confirmation of recovery of an AE. For clinical laboratory items, this shall be the date of blood or urine sampling. In the case of death, this shall be the date of death.

Outcome:

The outcome of an AE will be selected from the following 6 categories (one only). If the subject died, the date of death will be recorded; if the subject's condition was ameliorated (recovering), unrecovered, or unknown, the date of outcome confirmation will be recorded.

- Recovered
- Ameliorated (recovering)
- Unrecovered
- Recovered but with sequelae
- Death
- Unknown (for some reason, a follow-up investigation could not be performed even once)

5.2 Eliciting and Reporting Adverse Events

The investigator or subinvestigator will periodically assess subjects for the occurrence of AEs. To avoid bias in eliciting AEs, subjects should be asked the nonleading question: "How have you felt since your last visit?" All AEs (serious and nonserious) reported by the subject must be recorded on the source documents and eCRFs provided by the sponsor. The name of an AE, date of onset, date of recovery, seriousness, severity, causal relationship to the IMP, and outcome will be recorded on the source documents and eCRF.

Adverse event and SAE collection is to begin after a subject has signed the ICF and continue until the end of trial date. Adverse events occurring in the screening period and Period 1 will be assessed in comparison with the subject's condition at the time of consent/screening, and AEs occurring in Period 2 and Period 3 (Cohort 1 and Cohort 1' (as necessary) [single administration period] only) will be assessed in comparison with the subject's condition at the start of Period 2. For subjects who were withdrawn from the

trial at the discretion of the sponsor and resume participation in the trial from Period 2 or 3, AEs and SAEs will be collected from the time participation in the trial resumes until the end of the trial. However, AEs that occur after withdrawal from the trial at the discretion of the sponsor and resolve before the date on which the subject provided his/her signature for re-consent will also be collected as far as possible. Adverse events will be assessed based on the following:

- Subjects who resume participation in the trial from Period 2: Adverse events occurring in the screening period will be assessed in comparison with their condition at the time of consent/screening when they first participated in the trial, and AEs occurring in Period 2 and Period 3 will be assessed in comparison with their condition prior to IMP administration in Period 2.
- Subjects who resume participation in the trial from Period 3: Adverse events occurring in the screening period and Period 3 will be assessed in comparison with their condition at the start of Period 2 when they first participated in the trial.

Use medical terminology in AE reporting. Adverse events should be reported as a single unifying diagnosis whenever possible or, in the absence of a unifying diagnosis, as individual signs or symptoms. Exacerbation or disease progression should be reported as an AE only if there are unusual or severe clinical features that were not present, or experienced earlier, or not expected based on the course of the condition.

A reported AE that undergoes a change in severity or seriousness must be reported as a new AE on the eCRF.

In addition, the sponsor must be notified immediately by e-mail of any IREs according to the procedure outlined below, in Section 5.3 Immediately Reportable Events. Special attention should be paid to recording hospitalization and concomitant medications.

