1.2.2.3 Phase 1 Multiple-dose Trial in Subjects With Schizophrenia (Japan 331-10-001)

A total of 21 subjects with schizophrenia received multiple doses of brexpiprazole at 1, 4, or 6 mg once daily for 14 days.

Overall, 90.5% of subjects (19/21) experienced AEs. The incidence of AEs by treatment group was 71.4% (5/7) in the 1-mg group, 100.0% (8/8) in the 4-mg group, and 100.0% (6/6) in the 6-mg group. The most frequently reported AEs (incidence \geq 5% of all subjects) were blood prolactin increased (38.1%, 8/21), blood creatine phosphokinase increased (14.3%, 3/21), nausea, nasopharyngitis, blood pressure increased, blood prolactin decreased, insomnia, and schizophrenia (9.5%, 2/21 each). The majority of events, including blood prolactin increased, were considered potentially related to the IMP. Serious adverse events of schizophrenia were reported in 2 subjects (1 each in the 1-mg and 4-mg groups), both of which led to discontinuation.

The trial results demonstrated the safety and tolerability of brexpiprazole at up to 6 mg in Japanese subjects with schizophrenia.

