1.2.2.5 Long-term Trial in Subjects With Schizophrenia (Japan 331-10-003)

This long-term trial conducted in Japan was an open-label trial to evaluate the safety and efficacy of long-term administration of brexpiprazole in subjects with schizophrenia, either continuing treatment from the dose-finding trial 331-10-002 (rollover subjects) or newly enrolled in this trial.

All efficacy endpoints, including PANSS total score and Clinical Global Impression-Severity of Illness (CGI-S) score, remained stable until Week 52.

The incidence of AEs was 85.2% in newly enrolled subjects, 80.6% in rollover subjects, and 83.6% in all subjects. The most frequently reported AE was nasopharyngitis (25.1%) in newly enrolled subjects, schizophrenia (26.5%) in rollover subjects, and nasopharyngitis (23.1%) in all subjects. Most AEs were mild or moderate in severity. No deaths were reported in this trial. The incidence of SAEs was 10.4% in newly enrolled subjects, 18.4% in rollover subjects, and 13.2% in all subjects. Serious adverse events reported in more than 1 subject were schizophrenia in newly enrolled and rollover subjects and dehydration, akathisia, and schizophrenia in all subjects. The incidence of AEs leading to discontinuation was 10.9% in newly enrolled subjects, 23.5% in rollover subjects, and 15.3% in all subjects. The most frequently reported AE leading to discontinuation was schizophrenia in newly enrolled subjects, rollover subjects, and all subjects. No clinically meaningful changes were noted in laboratory test values, vital signs, or ECGs in newly enrolled subjects, rollover subjects, or all subjects. The mean change in weight from Period 2 baseline to the final assessment (last observation carried forward [LOCF]) was 0.34 kg in newly enrolled subjects, 2.02 kg in rollover subjects, and 0.93 kg in all subjects. There was no marked difference in safety results between newly enrolled subjects and rollover subjects, indicating that switchover to brexpiprazole monotherapy from prior treatment with existing antipsychotic drugs has no significant impact on safety.

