- a) At least 1 subject experienced an IMP-related SAE or at least 2 subjects experienced a severe IMP-related AE. Adverse events associated with exacerbation of the underlying disease will be comprehensively assessed through discussions between the medical expert and the sponsor to determine the feasibility of progression to Cohort 2 (repeated administration period).
- b) At least 1 subject experienced IMP-related abnormal blood pressure (systolic blood pressure of < 80 mmHg).
- c) At least 1 subject experienced any of the following IMP-related abnormal ECGs:
 - i) QTc interval (QTcF) of > 500 ms (results at the central ECG laboratory)
 - ii) Prolongation in QTc interval (QTcF) by > 60 ms from baseline (predose in Period 2) (results at the central ECG laboratory)

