3.9.3.3 Documenting Reasons for Discontinuation

All subjects have the right to withdraw and the investigator or subinvestigator can discontinue a subject's participation in the trial at any time if medically necessary. In addition, subjects meeting the following criteria must be withdrawn from the trial. Only one reason for discontinuation (the main reason) can be recorded in the eCRF.

- Adverse event:
 - Continuation of IMP would place the subject at undue risk as determined by the investigator or subinvestigator
 - Safety concern possibly, probably, or likely related to IMP
 - SAE
 - Exacerbation or progression of the underlying disease

- Meeting the criteria for withdrawal before dose increase
- Subject decides to discontinue because of annoyance or discomfort due to a nonserious AE which is not otherwise determined to be an undue hazard
- Subject vomits within 12 hours after IMP administration
- Subject shows allergic reaction or hypersensitivity to brexpiprazole
- Withdrawal of informed consent by the legal representative of the subject
- Withdrawal of informed consent by the subject
- Lost to follow-up
- Pregnancy (see Section 5.5 Pregnancy)
- Investigator's or subinvestigator's decision (other than AE)
- Major protocol deviation
- Termination of all or part of the trial by the sponsor
- Other (record details)

If the subject discontinues IMP due to an AE, the investigator, subinvestigator, or other trial personnel, will make every effort to follow the event until the event is resolved or stabilized, or the subject is lost to follow-up or has died. The procedures in Section 5.7 Follow-up of Adverse Events must be followed.

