7.6.1 Adverse Events

All AEs will be coded by system organ class and the ICH Medical Dictionary for Regulatory Activities (MedDRA) preferred term. The incidence of the following events will be summarized:

- AEs occurring after administration of the QW formulation (treatment-emergent adverse events [TEAEs])
- TEAEs by severity
- TEAEs with an outcome of death
- Serious TEAEs
- TEAEs leading to discontinuation of the trial

The above summaries will also be prepared for TEAEs potentially causally related to the IMP.

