9.2 Adverse Events

All AEs will be coded by system organ class (SOC) and Medical Dictionary for Regulatory Activities (MedDRA version 23.1) preferred term (PT). If multiple occurrences of the same event are observed in the same subject during the same period, the highest severity will be used for analysis. The incidence of the following events will be summarized by SOC and PT:

- AEs occurring after administration of the QW formulation (treatment-emergent adverse events [TEAEs])
- TEAEs by severity
- TEAEs with an outcome of death
- Serious TEAEs
- TEAEs leading to discontinuations of the trial
- TEAEs by onset time (1-7 and 8-14 for Cohort 1 and Cohort 1' [as necessary]; 1-7 8-14, 15-21, 22-28, 29-35, 36-42 for Cohort 2)

The above summaries will also be prepared for TEAEs potentially causally related to the IMP.

Incidences of the AEs occurring in period 1 will be summarized by SOC and PT for subjects treated with conventional tablet.

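### Worsening of schizophrenia that is neither severe nor unexpected can be an adverse-event withdrawal with no AE record, so the table of TEAEs leading to discontinuation may undercount it

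*Protocol*

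**What the plan says.** **Reporting rule.** Protocol Section 5.2: "Exacerbation or disease progression should be reported as an AE only if there are unusual or severe clinical features that were not present". The sentence goes on to offer prior experience and expectedness from the course of the condition as alternatives. The same section fixes what AEs are judged against: the condition at consent or screening for the screening period and Period 1, and the condition at the start of Period 2 for Periods 2 and 3.

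**Withdrawal rule.** Protocol Section 3.9.3.3 states that "subjects meeting the following criteria must be withdrawn from the trial". Under the adverse-event reason it lists "Exacerbation or progression of the underlying disease", with no qualifier on severity, novelty or expectedness. Only the main reason is entered in the eCRF.

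**Outputs.** SAP Section 7.1 tabulates withdrawals in each period by primary reason. Protocol Section 7.6.1 ("TEAEs leading to discontinuation of the trial") and SAP Section 9.2 ("TEAEs leading to discontinuations of the trial") count recorded AEs with onset after the QW formulation. Subjects whose CGI-S or CGI-I worsens are listed, without an incidence (Protocol Section 7.8.1, SAP Section 13.1).

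**The concern.** The withdrawal reason and the AE record rest on different tests. The disposition table draws on the first and the TEAE discontinuation table on the second. Where worsening meets the withdrawal rule but not the reporting rule, the two tables disagree, and neither document says how to reconcile them.

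Tolerability is a stated objective, the trial is open-label, and there is no control group, so the AE summaries are a main source of evidence on it. Worsening of the underlying disease matters in this programme. Of the long-term Japanese trial, Protocol Section 1.2.2.5 says: "The most frequently reported AE leading to discontinuation was schizophrenia in newly enrolled subjects, rollover subjects, and all subjects". An output on tolerability-driven withdrawal should not depend on how a site reads one sentence in Section 5.2.

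**Working it through.** No figure in the plan needs reproducing here. The check is a comparison of texts, followed by a statement of scale.

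**Step 1. Apply both rules to the same event.** The Section 5.2 sentence can be read in two ways. On the strict reading, severe features must also be new to the subject. On the loose reading, it is enough that severe features were absent at the start of Period 2. Take a subject who is withdrawn for exacerbation after a QW dose.

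| Worsening | Section 5.2: report as AE? | Section 3.9.3.3: reason | Result |
|---|---|---|---|
| Unusual or severe, and new or unexpected | Yes, on either reading | Adverse event | Tables agree |
| Severe, but seen in earlier episodes and expected | No (strict) or yes (loose) | Adverse event | Depends on the site |
| Neither unusual nor severe | No, on either reading | Adverse event | Disposition counts it, TEAE table does not |

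The third row does not depend on the reading. The second adds variation between sites, of which about 20 are planned (Protocol Synopsis).

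**Step 2. Look for a rule that closes the gap.** Section 5.1 treats a laboratory value that leads to discontinuation as an AE. There is no matching rule for disease worsening.

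**Step 3. Scale of one missed case.** Section 3.3.1.1 targets 20 completers per cohort, so withdrawals may come on top of 20.

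- Denominator 20: 1/20 = 5.0 percentage points.
- Denominator 21 (one withdrawal added to 20 completers): 1/21 = 4.8 points.
- Exact 95% intervals: 0/20 gives 0 to 16.8%; 1/20 gives 0.1 to 24.9%.

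**Step 4. How often a withdrawal for worsening might occur.** The documents give no rate for this trial, so the risk p is an assumption. For 20 subjects, the expected number is 20 × p and the chance of at least one is 1 − (1 − p)^20.

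| Assumed p | Expected number | Chance of at least one |
|---|---|---|
| 2% | 0.4 | 33% |
| 5% | 1.0 | 64% |
| 2/21 = 9.5% | 1.9 | 86% |

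The last row borrows the rate in Protocol Section 1.2.2.3: "Serious adverse events of schizophrenia were reported in 2 subjects (1 each in the 1-mg and 4-mg groups), both of which led to discontinuation". The table concerns all withdrawals for worsening, not unrecorded ones. If a share f goes unrecorded, the expected number missed is 20 × p × f. The documents do not give f, so at p = 5% the figure lies anywhere from 0 to 1.0.

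**The case against.** The best defence is that the protocol, read as a whole, expects these events on the AE form. Section 3.9.3.3 sends AE discontinuations to the follow-up procedures of Section 5.7, which work from the AE eCRF. Section 5.1 defines an AE broadly and makes hospitalisation, or its prolongation, a criterion for seriousness; Section 5.3 requires every SAE to be reported. Section 3.8.1 a) speaks of such events as AEs: "Adverse events associated with exacerbation of the underlying disease will be comprehensively assessed through discussions between the medical expert and the sponsor". On this view Section 5.2 filters out only expected, non-severe fluctuation.

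Much of this stands for severe and serious worsening. It does not close the gap for the rest, because the route through Section 5.7 presupposes an AE record that Section 5.2 tells the site not to make.

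A reader might infer more than the documents support:

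- *That the tables leave out worsening of schizophrenia altogether.* Section 5.2 admits severe or unexpected worsening, and both cases in Section 1.2.2.3 were serious, so their like would probably be captured here. The documents do not say that relapses usually repeat earlier symptoms.
- *That rates from the long-term trial apply.* That trial was assessed to Week 52. Here QW exposure is two single doses or five weekly doses, and other antipsychotics may continue (Section 4.3).
- *That the QW formulation will look better than in the earlier trials.* The AE-recording rule of those trials is not given, and no cross-trial comparison is planned.
- *That the decision to progress to Cohort 2 is compromised.* The trigger in Section 3.8.1 a) is IMP-related serious or severe events, the kind most likely to be kept.
- *That no other trace remains.* Disposition tables, discontinuation listings, CGI listings and concomitant medication listings would still show the case, though not as a TEAE.

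**Conclusion.** The concern holds as a conflict between Sections 5.2 and 3.9.3.3. Its consequence is that TEAEs leading to discontinuation may undercount withdrawals for non-severe or expected worsening, and may disagree with the adverse-event count in disposition. Each missed case is worth about 5 percentage points in a cohort of about 20. The number of such cases cannot be estimated from the documents and could be zero.

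This rests on two assumptions: that the eCRF reason categories follow the headings of Section 3.9.3.3, and that sites apply Section 5.2 as written. It is worth correcting because a stated rule can understate a tolerability output and the correction is cheap.

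A related inconsistency needs attention. Section 3.9.3.2 lets a subject whose event is associated with exacerbation stay in the trial at the investigator's discretion, while Section 3.9.3.3 lists exacerbation among criteria that require withdrawal.

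**What to change.** 1. Amend Protocol Section 5.2 so that any worsening of schizophrenia that leads to withdrawal, judged against the comparison condition already set in that section, is recorded as an AE with severity and causality. Redraft the sentence so that it is clear whether severe features must also be new.
2. Add a data check that every discontinuation with an adverse-event reason has a linked AE record.
3. In the SAP, reconcile the adverse-event count in the disposition-reason tables with the table of TEAEs leading to discontinuation, and explain any difference. Restrict this to periods after the first QW dose, since Period 1 AEs are outside the TEAE definition.
4. Reconcile Protocol Sections 3.9.3.2 and 3.9.3.3 on exacerbation. Which rule should apply is for the sponsor to decide.

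Making every small CGI-I worsening an AE is not needed for this purpose.

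The cost of items 1 to 3 is a short amendment to Section 5.2, one eCRF consistency check and a few lines in the SAP. AE incidence may look slightly less favourable.
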